### ***Definition of Primary and Secondary Outcomes/Endpoints***

Because qualitative research is by nature exploratory, we have not defined outcomes for the focus group discussions with practice staff (**Aim 1**); however, we will use the Promoting Action on Research Implementation in Health Services (PARIHS) framework to guide these discussions about facilitators and barriers to WE CARE implementation. Key areas of exploration will be (1) evidence: attitudes and beliefs about evidence of the WE CARE system; (2) context: organizational, systemic, and sociopolitical features that promote or hinder implementation of WE CARE; and (3) facilitation: attributes of the facilitation that supported or impeded the implementation, and needed adaptations.

Primary outcomes for **Aim 2** include the following:

- *Identification of unmet needs and provision of referrals.* Previously utilized forms will be used during baseline and follow-up questionnaires to measure whether practitioners provided families resource handouts.
- *Parental enrollment in community-based resources.* Baseline and follow-up questionnaires to measure enrollment in community resources.
- *Process measures.* Data will be collected on adherence to clinic visits (appointments kept, cancelled, and no-show). We will collect data on medications adherence in two ways. First, we will collect laboratory markers that are commonly affected by HU, including hemoglobin and hemoglobin F levels, white blood cell and absolute neutrophil counts, and MCV. We will also collect data on prescriptions written and filled for HU and penicillin through EHR review and parent report.
- *Health outcomes:* Data on vaso-occlusive episodes, acute chest syndrome and sepsis will be collected from the EHR at 6-month- and 12-month follow-up. Quality of life will also be assessed through both the PedsQL, which has been validated in children with sickle cell disease and is responsive to change, and the PedsQL Sickle Cell Disease Module.
- *Healthcare utilization outcomes:* Data on emergency department visits, hospitalizations, and clinic visits will be collected from the EHR at baseline and 12-month follow-up. We have chosen

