emergency department visits as our primary outcome because it has been extensively, and commonly, used as a measure of lack of outpatient care and non-adherence to treatment regimens in this population. We will also calculate ED reliance (clinic visits kept / clinic visits kept + ED visits), as it has been used to discriminate frequent emergency department users.

Because qualitative research is by nature exploratory, we have not defined outcomes for the qualitative interviews with parents of children with SCA (**Aim 3**). Qualitative interviews will aim to examine parents' perceptions of factors that promote or hinder effective management of their child's SCA.

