Eligible study participants will be identified by the front desk staff and research staff at each clinic. Prior to each clinic session, the research staff will identify potentially eligible study subjects by reviewing the daily appointment list. We will also ask front desk personnel to assist us in identifying potential subjects, if they are willing, and, in some sites, to assist in handing out informational flyers. If a family is identified as likely to meet eligibility criteria, a member of the study team will approach potentially eligible parents in a private location at the practice, such as an exam room. If the parent is eligible for the study, a study team member will review the study with him/her. Informed consent will be obtained via written consent. The original hard copies of the ICFs will be stored in a locked file in a locked room in the hematology research space at that site. Each clinical site will maintain a tracker linking each patient to a unique subject ID number, which does not contain any combination of information that allows the identification of a subject; this tracker will not be shared outside that clinical site. Participants will be provided with a copy of their signed informed consent form.

Data will be collected from parents primarily from parent-administered surveys at enrollment and at follow-up which will occur one year post-index visit. These surveys will be completed using a study tablet (e.g., iPad) and backed up on to a HIPAA-compliant Boston Medical Center installation of REDCap, which is backed up on the secure, password-protected Boston University Medical Campus server. To complete these surveys, subjects will enter their unique ID number. A brief telephone interview will be conducted 3, 6, and 9 months post-enrollment to ascertain unmet needs, contact and enrollment in community-based resources, and parent report of prescription refills for penicillin or hydroxyurea. A hair cortisol sample will also be collected from the parent at enrollment and 1-year follow-up. Finally, site research staff will collect data from the electronic health record (EHR) on child health outcomes (i.e., adherence to clinic visits, medication adherence, ED visits, hospitalizations, vaso-occlusive episodes, acute chest syndrome, and infections). Data from the EHR will be collected three times (baseline, 6-months post-enrollment, and 12-months post-enrollment).

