*\*Research Electronic Data Capture (REDCap) is a research focused, electronic web-based data capture system. REDCap is a data collection tool and allows for storage and management of both surveys and databases. REDCap is a secure storage system and meets HIPAA compliance standards. REDCap software will be used to facilitate parent consents, questionnaires, and forms.*

**Materials.** The research data will include questionnaires completed by parents/caregivers both in-person and via telephone, parent hair cortisol samples, and medical chart review. Only trained project staff at each clinical site will have access to participants' identifying information.

For the hair cortisol samples, we will be following the hair collection protocol developed by [name] from the University of Massachusetts (UMASS). Hair will be cut at the level of the scalp from 2-3 locations and cut to 3cm at the distal end. Hair samples will be placed directly into a plastic vial; each vial will be labeled by an ID number uniquely linked to each study subject (see below). Hair cortisol is stable at room temperature indefinitely, thus vials will be stored in a locked file cabinet.

For the *medical chart review*, existing trained research staff members at each study site, will collect the data. We decided to use existing research staff for the data collection component of the study since getting chart review credentialing is difficult at each of the study sites. At baseline and 12-month follow-up, medical charts will be reviewed in order to determine the number of appointments kept versus cancelled or no-show, the number of days covered by prescription refills for penicillin and hydroxyurea, and blood tests for monitoring hydroxyurea (including WBC, HB F%, and MCV). At 6-month and 12-month follow-up, medical charts will be reviewed in order to determine the frequency of vaso-occlusive episodes, acute chest syndrome, and sepsis diagnoses.

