***Aim 2. Obtain population-specific empirical estimates of study parameters to plan a pragmatic large-scale cluster RCT.*** We will summarize the number of parents contacted, lost to follow-up, refusing participation, and enrolled. We will examine this by gender (e.g., father vs. mother). We will note reasons for refusals. We will determine parents' recruitment and attrition rates and receipt of WE CARE using descriptive statistics. We will also determine the data collection completion rate, including hair cortisol, for each data time point (baseline, 3-, 6-, 9-, and 12-month follow-up) via descriptive statistics. Each outcome and process variable described above will be first transformed into its final composite value/score. We will calculate within-group mean and standard deviation of our SDoH, process, mediator and health utilization and health outcome variables. We will also break down the intervention group into two subgroups differentiated by whether parents enrolled in resources at follow-up, and explore any differences. An intention-to-treat approach will be used to explore differences between the intervention and control groups. We will also report all data disaggregated by gender. Two independent sample t-test and chi-square tests will be used to determine bivariate differences. Mixed effects regression models will be used to estimate the effect size of the intervention on SCA outcomes accounting for baseline differences in sociodemographics, types of SDoH, cumulative needs, receipt of services, and *a priori* determined covariates (i.e. sociodemographic characteristics). To explore potential moderators for the intervention effect at the parent, child and family levels (e.g., gender, race, ethnicity, age, language, household income), we will use Rothman's methodology; specifically, we will conduct stratified analyses for each potential moderator followed by using standard interaction terms in our models. We will also explore mediation of our hypothesized potential mediators between SDoH and the intervention with each SCA health outcome using the approach recommended by MacKinnon, Lockwood, and Williams. We will account for the clustering by study site by calculating the intraclass correlation.

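### The Aim 2 effect-size model does not name the child's baseline ED use, although ED visits are the primary outcome and have a baseline record pull

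*Combined protocol and SAP*

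**What the plan says.** **Model.** Data Analysis Plan, Aim 2, sets the mixed effects regression this task: "estimate the effect size of the intervention on SCA outcomes accounting for baseline differences in sociodemographics, types of SDoH, cumulative needs, receipt of services". A further group of covariates, fixed in advance, closes the list and is worded as "determined covariates (i.e. sociodemographic characteristics"). The section does not say whether the response is the follow-up value, a change, or a series of repeated measures.

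**Outcome.** Definition of Primary and Secondary Outcomes/Endpoints chooses "emergency department visits as our primary outcome because it has been extensively" used in this population. Statistical Power and Sample Considerations also labels ED visits primary.

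**Baseline data.** The endpoints section states: "Data on emergency department visits, hospitalizations, and clinic visits will be collected from the EHR at baseline and 12-month follow-up". The Study 2 procedures list ED visits among the record items and add: "Data from the EHR will be collected three times (baseline, 6-months post-enrollment, and 12-months post-enrollment". Data Management Methods, Aim 2, repeats this. No section defines the period that the baseline pull covers.

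**Timing.** Description of Study Treatments has WE CARE fully in place at the two intervention sites before families enrol. The survey goes to all parents of SCA patients at every visit, whether or not they join the study.

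**Purpose.** The power section says the pilot will not be used to determine efficacy and that planning will rest on control-group estimates.

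**The concern.** The outcome's own baseline is usually the first covariate to consider in an adjusted comparison. Here it is due to be collected, yet the covariates that are spelled out do not include it. With 70 children per arm in four sites, the arms can differ by chance in prior ED use. That difference is error in the one effect estimate the pilot will produce; it is not bias across randomisations. The listed social covariates may remove part of it.

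The timing complicates the remedy. WE CARE is running before enrolment, so a look-back that ends at enrolment can include intervention time at the intervention sites. Adjusting for it could then remove part of the effect.

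**Working it through.** The plan has no figure of its own on this point: it gives no baseline ED rate and no baseline-to-follow-up correlation. Both are assumed below.

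**1. Chance imbalance in prior ED use**

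Inputs from Statistical Power and Sample Considerations: 35 families at each of 4 sites, so 70 per arm; cluster coefficient 0.01; 80% of controls with at least one ED visit. Assumption: the 80%, a follow-up figure, also holds at baseline, so p(1 - p) = 0.16.

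- Site part of the variance: 2 × 0.16 × 0.01 / 2 = 0.0016 (SD 0.040)
- Child part: 2 × 0.16 × 0.99 / 70 = 0.00453 (SD 0.067)
- Total: 0.00613, SD 0.078, or 7.8 points; child share 0.00453 / 0.00613 = 0.74
- Chance of a gap over 10 points: z = 0.10 / 0.078 = 1.28, two-sided probability 0.20 (simulated 0.16-0.18)

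**2. How much of a gap carries into the estimate**

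Assumed model: each child has a gamma-distributed ED rate (shape k = 1, 2 or 4; mean 4.0, 2.47 or 1.98 visits, so that 80% have at least one), and counts are Poisson. The child's rates before and after are correlated. With the same 80% in both periods, the slope of any later visit on any prior visit equals their correlation r.

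- Child-rate correlation 0.5-1: r = 0.07-0.44, so a 10-point gap carries 10 × r = 0.7-4.4 points
- Child-rate correlation 0.3: r = 0.04-0.11, so 0.4-1.1 points

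**3. Change in the variance of the risk difference**

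Simulated trials of four sites of 35, with a site effect on the ED rate calibrated to an ICC of 0.01 and linear adjustment for prior ED use. Monte Carlo error is about 1-2 points. Site differences either persist fully from baseline to follow-up or are redrawn independently.

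| Covariate | Child-rate correlation | Sites persist | Sites do not persist |
|---|---|---|---|
| Any prior visit (yes/no) | 0.3 | cut of about 2-6% | about neutral (loss of 0.4-1.1%) |
| Any prior visit (yes/no) | 0.5-1 | cut of 3-33% | loss of 0.5% to cut of 8% |
| log(1 + prior visits) | 0.3 | cut of 4-14% | loss of 1.5-2.5% |
| log(1 + prior visits) | 0.5-1 | cut of 7-41% | loss of 0.5% up to about 9% |

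The log form gains more when site differences persist, but it can lose when they do not. The yes/no form costs almost nothing in the bad case.

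The rows at 0.3 matter most for the fix proposed below. A window that ends before go-live is older for families who enrol late, and so probably less predictive.

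**4. Why a window ending at enrolment is unsafe**

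From the Study Timeline as it can be read, and assuming a 12-month look-back, the time t from go-live to enrolment is uniform on 0-15 or 3-18 months. The mean of min(t, 12) / 12 is then:

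- 0-15 months: (6 + 3) / 15 = 0.60
- 3-18 months: (5.625 + 6) / 15 = 0.775

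So 60-78% of the look-back would fall after go-live. This is an upper bound on exposure, because only families with an identified need are to receive resource sheets. If all of that time carried the full effect, adjusting for log(1 + prior visits) would shrink a true 25-point effect by 2-12 points. If half did, the shrinkage would be 1-5 points.

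**The case against.** **The point rests on silence.** A mixed model can carry baseline as a repeated measure, and the outcome is due at baseline and 12 months. That stands, and is why baseline is described here as unspecified. A reader might infer that the plan rules out baseline adjustment, but nothing in the text says so. It still gives a covariate list and no structure that would bring baseline in.

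**Little depends on it.** A covariate in the between-arm model changes no control-group mean, SD or attrition rate, and those are what the plan will use. This stands and sets the severity. The plan nonetheless promises an adjusted effect size.

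**The fix is not free.** Nothing says that the baseline pull reaches back before go-live. For a family enrolling 15-18 months after go-live, a 12-month pre-go-live window reaches back 15 + 12 = 27 to 18 + 12 = 30 months. Eligible children are aged 0-12 years, so any born after go-live have no pre-period. This stands and is costed below.

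**A tempting stronger reading** is that baseline adjustment would rescue the study's power. For 80% v 55%, two-sided 5%, and design effect 1 + 34 × 0.01 = 1.34, the effective number per arm is 70 / 1.34 = 52.2 and power is 78.7%. A correlation of 0.5 would raise the effective number to 52.2 / (1 - 0.25) = 69.7 and power to 89.2%. The documents give no such correlation, and the model above puts the yes/no value at 0.04-0.44. Nor does adjustment cure having two sites per arm.

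**Another** is that the record schedules contradict each other. One sentence says "Data on vaso-occlusive episodes, acute chest syndrome and sepsis will be collected from the EHR at 6-month- and 12-month follow-up", while the general statement has three pulls. The two can be read together, with items allotted to pulls. The chart-review list, which begins "At baseline and 12-month follow-up, medical charts will be reviewed in order to determine the number of appointments kept versus cancelled or no-show", does not mention ED visits, but other sections cover them. These are clerical matters.

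**Conclusion.** The point holds as a minor, low-cost improvement. The plan commits to a covariate-adjusted effect size, and the covariates it names leave out the primary outcome's own baseline.

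The gain is uncertain and probably small with the safe window. It depends on the assumed gamma-Poisson rates, the borrowed 80%, the ICC of 0.01, and whether site differences in ED use persist. None of these except the ICC is a baseline quantity or correlation that the documents supply. The documents do not support a claim that the omission biases the trial or changes any decision taken from it.

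**What to change.** In Data Analysis Plan, Aim 2:

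1. State how baseline enters the model. Add any prior ED visit (yes/no) as a covariate, in preference to log(1 + prior visits). Add likewise the baseline value of each other outcome that has one.
2. Take ED baseline from a fixed window ending at or before WE CARE go-live, with one calendar rule at all four sites, control sites included. Give children with a short or absent pre-period a stated category of their own.
3. If that window cannot be abstracted, say so and leave ED baseline out of the main model. Do not substitute a window ending at enrolment.

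While editing, state which outcomes have a baseline pull, and list ED visits in the chart-review paragraph.

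Cost: one covariate, a written window rule and some extra record look-back, with no added visits or families. The price is an older, less predictive baseline for late enrollees and missing pre-periods for the youngest children.

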## Preliminary Studies

### **Family-centered approach for addressing SDoH for low-income children utilizing existing clinical infrastructure: the WE CARE Model.**

Our extensive groundwork has demonstrated that a family-

centered screening and referral intervention that relies on parental desire for assistance administered during pediatric preventive care visits led to increased provider referrals for, and parental receipt of, community resources. WE CARE (Well-Child care visit, Evaluation, Community Resources, Advocacy, Referral, Education) was efficacious in connecting families to community resources and resulted in

higher parental employment, receipt of fuel assistance and childcare, and lower odds of living in a homeless shelter, thereby reducing material need when tested in pediatric primary care clinics.

Ongoing work is providing a better understanding for the barriers (e.g., staff burden, lack of time and/or resources) and facilitators (e.g., clinic culture and leadership) for implementing this relatively simple intervention in general pediatric practice. This is necessary given the well-known challenge of incorporating efficacious innovations into routine medical practice. *Our WE CARE studies so far have focused on children without medically complex conditions and have been implemented only in primary care pediatric practices. Our studies to date have not been designed to measure the impact of WE CARE on child health outcomes, since they have targeted parents with healthy children.*

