### ***Exclusion Criteria***

- Staff at the four sites who are unable to converse in English or Spanish or are under 18 years of age.
- Parents  $< 18$  years of age, parents with children with SCA who are 13 years of age or older, parents whose child does not take daily penicillin or hydroxyurea, foster parents, caregivers who speak neither English nor Spanish, and caregivers previously enrolled in the study.

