***Description of Study Treatments or Exposures/Predictors***

**WE CARE SDoH Screening and Referral intervention:** WE CARE is a relatively simple intervention that has two key components: (1) the WE CARE SDoH Screening Survey and (2) SDoH Community Resource sheets. The intervention will be fully implemented at two of four study sites, after which subjects will be enrolled to collect the outcomes described on pages 7-8, *Definition of Primary and Secondary Outcomes/Endpoints*.

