**Table 1. Summary of the WE CARE Components.**

Key Components:	Description
WE CARE SDoH Screening Survey (see attachments)	Administered at all visits Identifies 6 unmet material needs and parent desire for assistance with: childcare, employment, food security, utilities (heating/cooling, water, electricity), housing, inadequate education 3 rd grade reading level; 0.92 test-retest reliability of original survey 
SDoH Community Resources	One-page information sheets listing available resources 5 th grade reading level

***Component 1: WE CARE SDoH Screening Survey.*** The survey consists of 12 questions designed to: (1) briefly identify 6 unmet material needs (e.g., childcare, employment, food security, household heat,

housing inadequate education) by self-report (e.g., “Are you employed?”) and (2) using a family-centered approach, determine whether parents would like assistance with each problem (i.e. “If no, do you want help?”). Parents wanting help will receive a resource referral (see below). The survey has been translated into Spanish. Because it is a component of the practice-wide implementation of the WE CARE SDoH screening and referral program, the survey will be given at all visits by the front desk staff to all parents of SCA patients who present to the pediatric hematology clinic—not solely to caregivers who enroll in the study. The front desk staff and/or research staff will instruct parents to complete the screener. Clinic staff will be trained to review the WE CARE SDoH survey at visits and to provide community resource information sheets to parents with needs (see below). The completed surveys will be scanned into the EHR.

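### The Aim 2 effect-size model adjusts for receipt of services, which WE CARE may already have changed at its two sites before families enrol

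*Combined protocol and SAP*

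**What the plan says.** The Aim 2 part of the Data Analysis Plan uses mixed effects regression to estimate the size of the intervention effect on SCA outcomes, "accounting for baseline differences in sociodemographics, types of SDoH, cumulative needs, receipt of services" and further sociodemographic covariates fixed in advance. The same paragraph plans unadjusted t-tests and chi-square tests and a separate mediation analysis.

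Four other places bear on when those covariates are measured:

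- **Order of events.** Under Description of Study Treatments or Exposures/Predictors: "The intervention will be fully implemented at two of four study sites, after which subjects will be enrolled to collect the outcomes".
- **Who is exposed.** The description of Component 1 says that "the survey will be given at all visits by the front desk staff to all parents of SCA patients", whether or not they join the study.
- **Who is excluded.** The parent exclusions end with "foster parents, caregivers who speak neither English nor Spanish, and caregivers previously enrolled in the study". Earlier screening or referral through WE CARE is not on the list.
- **What is measured at baseline.** Two Aim 2 primary outcomes are taken from the enrolment questionnaire as well as at follow-up. For referrals: "Previously utilized forms will be used during baseline and follow-up questionnaires to measure whether practitioners provided families resource handouts". For resource enrolment: "Baseline and follow-up questionnaires to measure enrollment in community resources".

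The section on statistical power states that the pilot will not be used to judge efficacy and that control-group estimates will feed the later power calculation.

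**The concern.** A covariate protects an effect estimate only if the intervention cannot have altered it. Here baseline means the day a family enrols, and at the two WE CARE sites that day comes after the programme is running for everyone. A family may have been screened, given a resource sheet and connected to a service at an earlier visit. Receipt of services is what WE CARE is built to change: Preliminary Studies reports that it connected families to resources, "thereby reducing material need when tested in pediatric primary care clinics".

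If receipt is already higher at the WE CARE sites because of WE CARE, adjusting for it removes whatever part of the benefit ran through that early receipt. The adjusted and unadjusted estimates would then differ for a reason other than chance imbalance, and a reader could not tell which. It also blurs the total effect with the direct effect, which the planned mediation analysis is meant to separate.

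**Working it through.** The plan states no figure for this adjustment, so there is none to reproduce. The check has five steps.

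**1. Which value of receipt enters the model?** The sentence allows two readings.

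- Baseline governs the whole list. Receipt is then the enrolment value, which follows implementation.
- Baseline governs sociodemographics only. Receipt is then a later value (it is also asked about at 3, 6, 9 and 12 months), and the model conditions on a mediator.

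No section limits receipt to values from before first exposure.

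**2. How many families could be exposed before enrolment?** By column count in the Study Timeline, assessment of implementation starts in Year 1 Q3 and accrual runs from Year 1 Q4 to Year 2 Q4. That places accrual at months 9 to 24. Assumed: go-live at month 6 or 9, and a visit every 3 or 6 months. A family is exposed if the time from go-live to enrolment is at least one visit interval.

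| Go-live / interval (months) | Even accrual | Linearly declining accrual | All in first 6 months |
|---|---|---|---|
| 6 / 3 | 100% | 100% | 100% |
| 6 / 6 | (24−12)/15 = 80% | 0.80² = 64% | 50% |
| 9 / 3 | 80% | 64% | 50% |
| 9 / 6 | (24−15)/15 = 60% | 0.60² = 36% | 0% |

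With 35 families at each of two WE CARE sites, the possible range is 0 to 70 of 70.

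**3. How much of the effect could be lost?** Take a 25-point effect, the smallest ED difference in the power statement (80% against 55%). Let m be the share of the effect carried by receipt and s the share of induced receipt that precedes enrolment. Assumed receipt: pC = 20% in control, pT = 60% with WE CARE.

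- Effect of receipt itself: g = 25m/(pT − pC).
- Receipt at enrolment in the WE CARE arm: q = pC + (pT − pC)s.
- The coefficient on enrolment receipt is g in control and g(1 − pT)/(1 − q), which is no larger than g, in WE CARE.
- Loss = pooled coefficient × (q − pC), which is at most g(pT − pC)s = 25 × m × s.

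| Share via receipt (m) | g | s = 0 | s = 0.36 | s = 0.60 | s = 1 |
|---|---|---|---|---|---|
| 0.10 | 6 points | 0 | ≤0.9 | ≤1.5 | 2.5 |
| 0.25 | 16 points | 0 | ≤2.3 | ≤3.8 | 6.3 |
| 0.50 | 31 points | 0 | ≤4.5 | ≤7.5 | 12.5 |

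Within this model the adjusted estimate at m = 0.25 is 25.0, 23.3, 21.9 and 18.8 points across the row. If induced receipt is spread evenly over families, s cannot exceed the exposed share in step 2. It will be lower, because being screened is not the same as receiving a service. The m = 0.50 row needs receipt alone to cut ED prevalence by 31 points, which is extreme. If receipt also marks higher need, the loss shrinks. With receipt 20 points commoner in high-need families and need adding 20 points to ED prevalence, the m = 0.25, s = 1 estimate is 20.8. On the second reading of step 1, s is in effect 1.

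**4. Scale against sampling error.** With the plan's cluster coefficient of 0.01, the design effect is 1 + 34 × 0.01 = 1.34. The standard error of the ED difference is √[(0.8×0.2 + 0.55×0.45)/70 × 1.34] = 8.8 points. Every loss in the first two rows is below one standard error, but it is a bias and would not average out with more families.

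**5. Needs and prior ED visits.**

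- *Needs.* If half the families are high-need, the chance gap between arms has standard deviation √(2×0.25/70 × 1.34) = 0.098. If high need adds 10 to 20 points to ED prevalence, a one-SD gap moves the unadjusted estimate by 1 to 2 points.
- *Prior ED visits.* The plan has "Data on emergency department visits, hospitalizations, and clinic visits will be collected from the EHR at baseline and 12-month follow-up". If the baseline extraction looks back 12 months (assumed), 41% to 78% of that window falls after go-live under the step 2 timings, for even or declining accrual. A gamma-frailty count model (80% against 55%, full effect from go-live, all assumed) loses about 1 to 2 points when prior and later ED use correlate at 0.12, and 2 to 4 points at 0.27.

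**The case against.** The strongest reply is that the size is undetermined. Go-live, visit interval, accrual shape, receipt rates and the mediated share are all assumed, and the range includes no loss at all. The timeline has no go-live row, and pre-implementation data collection overlaps the assessment row in Year 1 Q3. This stands. The documents show that the covariate can be post-exposure, not that it is or for how many families.

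A second reply is that this is one exploratory estimate in a pilot. The unadjusted comparisons remain, efficacy is disclaimed, and control-group estimates, which this bias cannot touch, set the later power. This also stands, and it keeps the point minor.

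A third reply is that with two sites per arm, adjusting for needs is a reasonable defence against imbalance. This stands for needs and SDoH types. A reader might infer that they should be removed along with receipt, since they too are recorded after go-live. The material does not support that: step 3 concerns receipt only, no loss was computed for needs, and a one-SD chance gap in needs can shift the estimate by as much as the smaller losses above. It is a trade-off to display, not a defect to delete. The reply does not rescue receipt of services, which lies most directly on the causal path and matches a listed primary outcome.

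A reader might also infer that prior ED visits are a clean substitute covariate. They are not if taken from a look-back at enrolment, since part of that window is itself after go-live.

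**Conclusion.** The concern holds for receipt of services. On one reading the main model adjusts for an enrolment value that WE CARE may already have changed in one arm. On the other it adjusts for a mediator measured later. Either way the adjusted effect can understate the total effect.

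On the enrolment reading the loss is zero if no induced receipt precedes enrolment. If 36% to 100% of it does, and a tenth to a quarter of the effect runs through receipt, the loss is at most about 1 to 6 points of 25. On the follow-up reading the same two shares give 2.5 to 6.3 points. These figures rest on assumed go-live, visit spacing, accrual shape and receipt rates, and on a simple linear model.

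A reader might infer that the pilot's effect estimate is known to be biased, or that planning of the later trial is compromised. The documents support neither: prior exposure is not quantified, and the later power calculation uses control-group estimates. Severity is minor.

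**What to change.** In the Aim 2 analysis text:

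1. Remove receipt of services from the main intervention-effect model. Keep it for the planned mediation analysis, and report the model that includes it as a sensitivity analysis.
2. State when needs, SDoH types and receipt are measured relative to a family's first WE CARE exposure, and which covariates the word baseline covers.
3. Report the effect estimate with and without enrolment-time needs and SDoH types, in both arms alike.
4. If prior ED visits from the enrolment look-back are added, report with and without them too, and say that part of the window may follow go-live.

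The cost is analysis-plan wording and a few extra model runs. No new data collection is needed. If the enrolment values prove to be truly pre-exposure, almost nothing is lost, because the fuller model is still reported.
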